# **20.4 Publication**

Study contributors (sites) may publish their own data independently from COVIDRIVE upon informing COVIDRIVE and acknowledgement of funding. Co-authorship will be defined following the ICMJE (International Committee of Medical Journal Editors) criteria and the Good Publication Practice (GPP). All publications will be open-access.

# 21 FUNDING

This study is partially funded by [Study Requestor].

The following study sites (hospitals) receive additional funding from other sources:

Study site (hospital)	Additional funding source

Study sites (hospitals) not listed did not receive additional funding. In those sites, the study is solely funded by [Study Requestor].

# ANNEX 1: VACCINE-ASSOCIATED ENHANCED DISEASE (VAED)

VAEDs are modified and severe presentations of clinical infections affecting individuals exposed to a wild-type pathogen after having received a prior vaccine against the same pathogen [1]. VAED has been observed in the past following administration of measles and RSV vaccines [2]. VAED is a theoretical concern for COVID-19 vaccines, based on observations from other respiratory viruses and from animal models of highly pathogenic coronaviruses [3]. While the underlying potential mechanisms for VAED are unclear, VAED always involves a memory response primed by vaccination and appears to target the same organs as wild-type infections [3]. Particular concerns include the potential for (inactivated whole-virus) vaccines to elicit antibody-dependent enhancement (ADE) of infection or vaccine-associated enhanced respiratory disease (VAERD) upon SARS-CoV-2 infection [4], although neither has been observed in clinical trials so far. Studying VAED on an individual patient level is challenging, as no confirmatory tests to diagnose VAED exist, and distinguishing vaccine failure from VAED among vaccinees is difficult.

VAED may be studied on a population level by comparing the occurrence and presentation of severe disease among vaccinated and non-vaccinated patients. VAED through ADE is postulated to occur with low levels of neutralising antibodies, and where non-neutralising or poorly neutralising antibodies increase the subsequent viral entry into cells, thereby intensifying the infection [5]. The effect of waning antibody titers after vaccination on ADE is unknown [6]. If neutralising antibodies wane over time, an association between time since vaccination and the risk of developing severe disease may be observed. Therefore, CVE should be studied against different levels of COVID-19 disease severity by time since vaccination.

Further information on VAED including possible pathophysiologic pathways is provided by Munoz et al. [3].

# The following form should be used to capture clinical and laboratory features of patients with critical COVID-19 disease admitted to the ICU.

#### **Section A: clinical features**

Please complete the tables below concerning the patient's condition during ICU stay.

During ICU admission, did th patient have any measurem rest of:		If yes, please provide the following details:
a respiratory rate ≥ 30 per minute?	□ No	
	🗆 Yes	
an oxygen saturation ≤ 93%	🗆 No	
on room air?	🗆 Yes	
a systolic blood pressure	🗆 No	
<pre>< 90 mmHg or a diastolic blood pressure < 60 mmHg?</pre>	□ Yes	
fever $\geq$ 39.3°C?	🗆 No	
	□ Yes	Total number of days:
a heart rate ≥ 125 beats per	🗆 No	
minute?	🗆 Yes	
During ICU admission, did th patient ever require:	e	If yes, please provide the following details:
non-invasive supplemental	🗆 No	
oxygen?	🗆 Yes	Total number of days:
respiratory ventilator	🗆 No	
support or ECMO  ?	🗆 Yes	Total number of days:
treatment with vasopressors?	□ No	
	□ Yes	Total number of days:
-	-	exhibit signs or symptoms of new/worsening dysfunction in
any of the following categorie	5?	
Gastrointestinal disorders		
Acute liver failure	🗆 No	□ Yes
Acute renal failure	🗆 No	□ Yes
Renal replacement therapy	🗆 No	□ Yes
Neurological disorders		

 Extracorporeal membrane oxygenation

						COVIDINIVE
Encephalopathy	🗆 No	🗆 Yes				
Convulsions/seizures	🗆 No	🗆 Yes				
Meningitis	🗆 No	🗆 Yes				
Altered level of	🗆 No	🗆 Yes				
consciousness						
Guillain-Barre Syndrome	🗆 No	🗆 Yes				
Cerebrovascular stroke	🗆 No	🗆 Yes				
Other	🗆 No	🗆 Yes	If yes, specify:			
Respiratory disorders						
Acute respiratory distress	🗆 No	🗆 Yes				
syndrome (ARDS)			If the second states to all			
Pneumonia	🗆 No	□ Yes	If yes, radiological confirmation?	🗆 No	🗆 Yes	
Acute respiratory failure	🗆 No	🗆 Yes	commution:			
Other	🗆 No	🗆 Yes	If yes, specify:			
Cardiac disorders						
Myocardial infarction	🗆 No	🗆 Yes				
Arrhythmia (new onset)	🗆 No	🗆 Yes				
Ischemic heart disease	🗆 No	🗆 Yes				
Myocarditis, pericarditis	🗆 No	🗆 Yes				
Stress cardiomyopathy	🗆 No	🗆 Yes				
Microangiopathy	🗆 No	🗆 Yes				
Other	🗆 No	🗆 Yes	If yes, specify:			
Vascular disorders						
Deep vein thrombosis	🗆 No	🗆 Yes				
Pulmonary embolus	🗆 No	🗆 Yes				
Limb ischemia	🗆 No	🗆 Yes				
Vasculitis	🗆 No	🗆 Yes				
Thrombocytopenia	🗆 No	🗆 Yes				
Other	🗆 No	🗆 Yes	If yes, specify:			
Others						
Multi-organ failure	🗆 No	🗆 Yes	If yes, specify:			
Multisystem inflammatory	🗆 No	🗆 Yes				
syndrome						

### **Section B: laboratory features**

Please provide the clinically significant laboratory results at ICU admission.

#### Date of sampling:

[dd/mm/yyyy]

	Clinically significant	
Test type/name	results?	Provide details for clinically significant results only
Creatinine	🗆 Yes	Results:
	🗆 No	Units:
	🗆 Unknown	Reference range:
Bilirubin	🗆 Yes	Results:
	🗆 No	Units:
	🗌 Unknown	Reference range:
Platelet count	$\Box$ Yes	Results:
	🗆 No	Units:
	🗌 Unknown	Reference range:
Lymphocytes (i.e.	□ Yes	Results:
CD4, CD8 counts)	🗆 No	Units:
	🗆 Unknown	Reference range:
Cytokines	🗆 Yes	Results:
	🗆 No	Units:
	🗆 Unknown	Reference range:
Procalcitonin	🗆 Yes	Results:
	🗆 No	Units:
	🗌 Unknown	Reference range:
C-reactive protein	🗆 Yes	Results:
	🗆 No	Units:
	🗆 Unknown	Reference range:
Ferritin	🗆 Yes	Results:
	🗆 No	Units:
	🗆 Unknown	Reference range:
Lactate	□ Yes	Results:
dehydrogenase (LDH)	🗆 No	Units:
	🗆 Unknown	Reference range:
D-dimer	🗆 Yes	Results:
	🗆 No	Units:
	🗆 Unknown	Reference range:
Prothrombin time (PT)	🗆 Yes	Results:
	🗆 No	Units:
	🗆 Unknown	Reference range:
Partial thromboplastin	□ Yes	Results:
time (PTT)	🗆 No	Units:
	🗆 Unknown	Reference range:
International	□ Yes	Results:
Normalized Ratio	🗆 No	Units:
(INR)	🗆 Unknown	Reference range:
Fibrinogen	□ Yes	Results:
	🗆 No	Units:
	🗆 Unknown	Reference range:

Test type/name	Clinically significant results?	Provide details for clinically significant results only
PaO2/FiO2	🗆 Yes	Results:
	🗆 No	Units:
	🗆 Unknown	Reference range:
PaCO2	🗆 Yes	Results:
	🗆 No	Units:
	🗆 Unknown	Reference range:
рН	🗆 Yes	Results:
	🗆 No	Units:
	🗆 Unknown	Reference range:
SpO2/FiO2	□ Yes	Results:
	🗆 No	Units:
	🗆 Unknown	Reference range:

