#### 14.3 Exploratory objectives

#### « Exploratory objectives 1, 2, 3 and 4 are stratifications to the co-primary objectives.»

- To estimate brand-specific CVE against hospitalisation due to laboratory-confirmed SARS-CoV-2 in severe acute respiratory infection (SARI) patients who have been vaccinated with at least 1 COVID-19 vaccine dose, compared to unvaccinated patients,
  - by severity level .
  - by calendar time .
- To estimate brand-specific CVE against hospitalisation due to laboratory-confirmed SARS-CoV-2 in SARI patients who completed a primary series vaccination, compared to unvaccinated patients,
  - by severity level .
  - by calendar time .
- 3. To estimate brand-specific CVE against hospitalisation due to laboratory-confirmed SARS-CoV-2 in SARI patients who previously completed a primary series with any COVID-19 vaccine and have received at least one additional COVID-19 vaccine dose , compared to (1) unvaccinated patients and to (2) patients who previously completed a primary series with any COVID-19 vaccine but who did not receive the last additional dose of interest ,
  - by severity level .
  - by calendar time .
- 4. [Only to support the interpretation of exploratory objective 3 ]: To estimate CVE across brands against hospitalisation due to laboratory-confirmed SARS-CoV-2 in SARI patients who previously completed at least a primary series with any COVID-19 vaccine but who did not receive the last additional dose of interest , compared to unvaccinated patients,
  - by severity level .
  - by calendar time .
- 5. To estimate the brand-specific effect of COVID-19 vaccination in patients who have [been vaccinated with at least 1 COVID-19 vaccine dose-- completed primary series vaccination] on length of hospital stay (in days) due to laboratory-confirmed SARS-CoV-2 admission compared with patients who [are unvaccinated have been vaccinated with at least 1 COVID-19 vaccine dose ...].
- 6. To study the potential occurrence of VAED by describing the clinical and laboratory features of critical COVID-19 disease  cases, by COVID-19 vaccine exposure status and time since vaccination. 

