#### 15.9.4 Critical COVID-19 disease

A critical COVID-19 disease case is defined as a COVID-19 disease case being admitted to the ICU. The clinical and laboratory characteristics of the critical COVID-19 disease cases will be described (Annex 1).

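### The Annex 1 ICU form cannot separate 'not hypoxaemic' from 'no room-air reading', and it keeps laboratory values only when an undefined judgement flags them

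*Protocol*

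**What the plan says.** Exploratory objective 6 (Section 14.3) is "To study the potential occurrence of VAED by describing the clinical and laboratory features of critical COVID-19 disease" cases, by vaccine exposure status and time since vaccination. Section 15.9.4 adds: "The clinical and laboratory characteristics of the critical COVID-19 disease cases will be described (Annex 1"). Annex 1 gives the reason for looking across groups: "VAED may be studied on a population level by comparing the occurrence and presentation of severe disease among vaccinated and non-vaccinated patients".

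The form that supplies these data is in Annex 1.

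- **Section A (clinical features)** covers the whole stay: "Please complete the tables below concerning the patient's condition during ICU stay". One item asks about any measurement of "an oxygen saturation ≤ 93" per cent on room air. The boxes are No and Yes. Separate items cover supplemental oxygen with days, ventilator "support or ECMO" with days, ARDS and acute respiratory failure.
- **Section B (laboratory features)** asks for clinically significant "laboratory results at ICU admission". Each test has a flag (Yes, No or Unknown). The column for result, units and reference range is headed "Provide details for clinically significant results only". PaO2/FiO2 and SpO2/FiO2 are in this list, under the same rule.

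The form does not define clinical significance and has no box for a test that was not done.

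**The concern.** The form feeds a description that is split by vaccine exposure, so it matters whether an entry means the same thing in each exposure group. Two features work against that.

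First, a patient on oxygen or ventilation throughout the ICU stay may never have a saturation reading on room air. The only literal answer is No, which is also the answer for a patient with normal saturation. If the share without a room-air reading differs between exposure groups, the Yes percentage differs for that reason alone.

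Second, a laboratory value is kept only when someone judges it significant. Medians and distributions then describe the flagged tail, not the patients. Without a stated criterion, the cut-off may vary across hospitals and countries.

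Neither loss can be repaired at analysis. A value that was never entered, or two states stored under one answer, cannot be recovered by a SAP.

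**Working it through.** The protocol states no figure for this objective, so there is none to reproduce. The check has two parts: what the form can distinguish, and how much the recording rule could matter under assumed inputs.

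**1. What the form can distinguish**

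| Patient state | Room-air item |
|---|---|
| Room-air reading of 93% or less | Yes |
| Room-air readings, all above 93% | No |
| No room-air reading during the ICU stay | No, or blank |

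Sections B and C offer Unknown; Section A does not.

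| State of a Section B test | Flag | Value kept? |
|---|---|---|
| Done, judged significant | Yes | Yes |
| Done, judged not significant | No | No |
| Not done | No or Unknown (the form does not say) | No |

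No other source fills the gap. Section 15.10 calls Annex 4 the complete dataset. It lists ICU admission, in-hospital death and discharge date, but no ICU laboratory values.

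**2. Laboratory values (all inputs assumed)**

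Let a test be normal with SD 1, mean 0 in one group and d in the other, with values recorded only above a cut-off t. The recorded mean is

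m(μ, t) = μ + φ(t − μ) / [1 − Φ(t − μ)].

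For d = 0.3 and t = 0: m(0.3, 0) = 0.3 + 0.3814/0.6179 = 0.917, and m(0, 0) = 0.3989/0.5 = 0.798. The recorded difference is 0.119 SD, which is 40% of the true 0.3 SD.

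| Cut-off t | Recorded difference, d = 0.3 | Share of truth | Recorded difference, d = 0.5 | Share of truth |
|---|---|---|---|---|
| −0.5 | 0.158 | 53% | 0.278 | 56% |
| 0 | 0.119 | 40% | 0.211 | 42% |
| 0.5 | 0.088 | 29% | 0.157 | 31% |
| 1 | 0.065 | 22% | 0.116 | 23% |

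For tests where low values are abnormal, the mirror image applies.

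Under a common cut-off the flag itself still carries information: at t = 0 and d = 0.3 it reads 50.0% against 61.8%. Under unequal cut-offs it does not. With no true difference and cut-offs of 0 and 0.5, the flag reads 50.0% against 30.9%, and the recorded means differ by 1.141 − 0.798 = 0.343 SD.

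**3. Room-air item (all inputs assumed)**

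Observed Yes = true hypoxaemia × (1 − share with no room-air reading). Take 90% truly hypoxaemic in both groups:

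- shares of 20% and 20%: 0.9 × 0.8 = 72% in both, gap 0;
- shares of 30% and 50%: 0.9 × 0.7 = 63% and 0.9 × 0.5 = 45%, gap 18 points;
- shares of 50% and 70%: 0.9 × 0.5 = 45% and 0.9 × 0.3 = 27%, gap 18 points.

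The gap arises only when the shares differ. It belongs to this one item, not to the form as a whole.

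**The case against.** The strongest reply is that the form contains overlapping information and the objective is modest. Three stronger readings are tempting, and the protocol supports none of them.

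- *Ventilated patients are counted as not hypoxaemic.* There is no scoring rule. The item covers any reading during the stay, so only patients with no room-air reading at all are affected. Oxygen, ventilator or ECMO support, ARDS and acute respiratory failure are recorded separately on the same form.
- *Laboratory features cannot be compared by exposure.* The flag is asked for every test and patient and can be tabulated, and flagged results carry value, unit and reference range. A markedly low PaO2/FiO2 is also the sort of result most likely to be flagged, so the rule probably loses least at the severe end.
- *The room-air item would create an apparent signal of enhanced disease.* That requires an assumed imbalance in respiratory support and an analyst who ignores the adjacent support items, where the same imbalance would show.

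Other parts of the reply also stand. Objective 6 is exploratory and worded as description. Annex 1 concludes that effectiveness should be studied by severity level and time since vaccination, and Section 15.9.2 defines severity from ICU admission and in-hospital death, not from this form. Nothing in the protocol shows that flagging would depend on vaccination status.

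The reply that the data management plan (Section 15.13.2), the SAP and mock report (Section 15.14) or training (Section 19.2) could define significance goes only part of the way. A criterion set there would standardise the flag. It would not bring back unflagged values, because the form asks for details of flagged results only. That study teams adapt the master protocol does not help unless they change this form.

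**Conclusion.** The point holds as a minor data-capture improvement. The room-air item merges two different states under No. Section B truncates laboratory values by an undefined judgement, so the only laboratory measure available for every patient by exposure is the flag. Both follow from the form itself and need no assumption.

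The size is not known from the protocol. Under the normal model with a common cut-off, recorded values show between 22% and 56% of a true difference of 0.3 to 0.5 SD. The room-air gap ranges from 0 to 18 points over the inputs tried and is zero when the shares without a reading are equal. These are illustrations, not predictions. Other items on the form partly compensate for the room-air problem, and no vaccine effectiveness estimate uses these data.

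**What to change.** In Annex 1, Section A, add a third answer to the saturation item, such as *no room-air reading (on oxygen/ventilated)*, and tabulate it separately from No.

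In Section B, record the result, unit and reference range for every listed test done at ICU admission, with *not done* as the alternative. Derive abnormality centrally from the reference range. The clinician's significance flag can stay as an optional tick.

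The cost is a revised form with one extra answer box, and modest extra transcription of values already measured, for ICU cases only. No new test is needed.

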#### Section C: other measurements

Please provide clinically significant laboratory, histopathological, and/or radiological results during ICU stay.

	Clinically significant			
Test type/name	results?	Provide	details f	or clinically significant results only
Histopathology/	🗆 Yes	Date(s):	:	
immunopathology	🗆 No	Results:	:	
of organs involved	🗌 Unknown			
Diagnostic imaging	Yes	Test	Date	Result
(Magnetic	🗆 No			
Resonance Imaging,	🗆 Unknown			
Computed				
Tomography,				
Ultrasound, Doppler,				
etc.)				
Other	🗆 Yes	Test	Date	Result w/units
relevant	🗆 No			
results	🗌 Unknown			

## **ANNEX 2: CHRONIC CONDITIONS**

Covariate	Definition
Chronic conditions	
Asthma	Any of the following diagnostic codes (ICD-10): J45, J46
	INCLUDING: predominantly allergic asthma, nonallergic asthma, status asthmaticus, acute severe asthma
	• EXCLUDING: acute severe asthma, chronic asthmatic (obstructive) bronchitis, chronic obstructive asthma, eosinophilic
	asthma, lung diseases due to external agents
Lung disease	• Any of the following diagnostic codes (ICD-10): A15-16, A19, A31.0, B33.4, E84.0, J40-44, J47, J60-70, J80-84, J85-86, J90-91, J92.9, J93-94, J95-99
	• INCLUDING: tuberculosis (pulmonary, miliary, but not that of other systems), atypical mycobacteria, cystic fibrosis, chronic obstructive pulmonary disease (COPD), bronchiectasis and other chronic sequelae of infections, chronic lung diseases due to external agents, interstitial lung diseases, pleural diseases, respiratory failure
	• EXCLUDING: acute respiratory infections, lung cancer, diseases of pulmonary circulation, pleural plaques without asbestos, previous uncomplicated pneumothorax
Cardiovascular disease	
 
Any of the following diagnostic codes (ICD- 10): A52.0, B37.6, I01-02, I05-09, I11.0, I13.0, I13.2, I20-25, I26-28, I30-43, I44-46, I48, I49.0, I49.5, I50-52, I70-71, Q20-Q28
 

	• INCLUDING: all conditions of heart and large vessels that are chronic or likely to have chronic sequelae, cardiovascular syphilis, endo-, myo- and pericarditis, rheumatic fever, chronic rheumatic heart diseases, congenital malformations, hypertensive (renal) diseases with heart failure, ischaemic heart diseases, diseases of pulmonary circulation, atherosclerosis, cardiomyopathies, most conduction disorders, heart failure, aortic aneurysms & dissecation, other heart diseases and their complications
	• EXCLUDING: uncomplicated hypertension, previous uncomplicated pulmonary embolism (with no lasting cardiac insufficiency), paroxysmal tachycardias, most cases of premature depolarization.
Hypertension	• Any of the following diagnostic codes (ICD-10): 110, 111.9, 112, 113.1, 113.9, 115
	INCLUDING: essential (primary) hypertension, secondary hypertension
	EXCLUDING: hypertensive heart/renal disease with (congestive) heart failure
Chronic liver disease	• Any of the following diagnostic codes (ICD- 10): B18, B19, K70.1-4, K70.9, K71.1, K71.3, K71.4, K71.6-9, K72.1,

	
 
K72.9, K73, K74, K75.2, K75.4, K75.8, K75.9, K76.1, K76.2, K76.5, K76.6, K76.9
 
INCLUDING: all conditions of the liver that are chronic or likely to have chronic sequelae
 
EXCLUDING: acute liver disease, liver cancer/metastasis, liver transplant
 

Chronic kidney disease	
 
Any of the following diagnostic codes (ICD- 10): I12-13, M10.30, N00-19, N20.0, N25-27, N28.0, N28.9, Q63.9, Z90.5
 
EXCLUDING: clinically nonsignificant kidney cysts
 

Type 2 diabetes	
 
Any of the following diagnostic codes (ICD-10): E11
 
INCLUDING: non-insulin dependent diabetes mellitus (adult-onset, maturity-onset, nonketotic, stable, type II, non-insulin-dependent diabetes of the young)
 

Cancer	
 
Any of the following diagnostic codes (ICD- 10): C00-97, D37-48, Z85, Z92.3, Z92.6
 
INCLUDING: all malignant neoplasms (both solid and haematologic) with potential to metastasise, either in treatment, active follow-up, or <5 years post curative treatment
 
EXCLUDING: benign & in situ neoplasms. Basal cell carcinomas. Any cancer previously treated with curative intent & in complete remission for ≥5 years.
 

Immunodeficiency (or organ transplant)	
 
Any of the following diagnostic codes (ICD-10): B20-B24, D80–84, D89, Z94
 
INCLUDING: human immunodeficiency virus (HIV) infections, immunodeficiencies and organ transplants, iatrogenic immunodeficiencies (systemic treatment of more than two weeks duration, in the three months preceding symptom onset, with any of the following: corticosteroid (≥20 mg prednisolone daily or equivalent), ciclosporin, tacrolimus, mycophenolate, methotrexate, azathioprine, tumor necrosis factor alpha (TNF-α) blockers and other biological or cytostatic drugs with immunosuppressive effect)
 
EXCLUDING: disorders of the immune system which do not lead to immunosuppression (e.g. some autoimmune conditions)
 

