#### Covariates

**Covariates:** Variables that are potential confounders and/or effect modifiers and will be collected at all study sites include age, sex, history of medical diagnosis for selected morbidities of interest (asthma, lung disease, cardiovascular disease, hypertension, chronic kidney disease, type 2 diabetes, cancer, immunodeficiency), body mass index (BMI), vaccination against pathogens causing COVID-19 like symptoms (influenza, pneumococcus), and calendar time.

Variables that will be *potentially additionally collected at certain study sites* include previous SARS-CoV-2 infection, any use of monoclonal antibodies and other anti-SARS-CoV-2 antibody products as either treatment or pre- or post-exposure prophylaxis prior to hospitalisation. precautionary health behavior, employment as health care worker (HCW), long-term care facility residence and smoking history.

C

VIDRIVE

Version 4.0

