#### 14.2 Secondary objectives

#### « All secondary objectives are stratifications to the co-primary objectives.»

- To estimate brand-specific CVE against hospitalisation due to laboratory-confirmed SARS-CoV-2 in SARI patients who have been vaccinated with at least 1 COVID-19 vaccine dose, compared to unvaccinated patients,
  - by SARS-CoV-2 genetic variants.
  - within populations of special interest (e.g. specific age groups, specific immunocompromised or chronic conditions, pregnant women).

- by time since last COVID-19 vaccine dose.
- by time between COVID-19 vaccine doses.
- To estimate brand-specific CVE against hospitalisation due to laboratory-confirmed SARS-CoV 2 in SARI patients who completed a primary series vaccination, compared to unvaccinated patients,
  - by SARS-CoV-2 genetic variants.
  - within populations of special interest (e.g. specific age groups, specific immunocompromised or chronic conditions, pregnant women).
  - by time since last COVID-19 vaccine dose.
  - by time between COVID-19 vaccine doses.
- 3. To estimate brand-specific CVE against hospitalisation due to laboratory-confirmed SARS-CoV-2 in SARI patients who previously completed a primary series with any COVID-19 vaccine and have received at least one additional COVID-19 vaccine dose , compared to (1) unvaccinated patients and to (2) patients who previously completed a primary series with any COVID-19 vaccine but who did not receive the last additional dose of interest ,
  - by SARS-CoV-2 genetic variants.
  - within populations of special interest (e.g. specific age groups, specific immunocompromised or chronic conditions, pregnant women).
  - by time since last COVID-19 vaccine dose.
  - by time between last two COVID-19 vaccine doses.
  - by number or type(s)  of the COVID-19 vaccine doses given prior to the last dose.
- 4. [Only to support the interpretation of secondary objective 3 ]: To estimate CVE across brands against hospitalisation due to laboratory-confirmed SARS-CoV-2 in SARI patients who previously completed at least a primary series with any COVID-19 vaccine but who did not receive the last additional dose of interest , compared to unvaccinated patients,
  - by SARS-CoV-2 genetic variants.
  - within populations of special interest (e.g. specific age groups, specific immunocompromised or chronic conditions, pregnant women).
  - by time since last COVID-19 vaccine dose.

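### Annex 2 admits acute events into the lung, cardiovascular and kidney conditions without a reference date, so a complication of the index stay can be counted as a baseline comorbidity and distort CVE in chronic-condition subgroups

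*Protocol*

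**What the plan says.** The Abstract (Covariates) describes the comorbidities as "history of medical diagnosis for selected morbidities of interest". Annex 4 sends sites to Annex 2 for the definitions, and Annex 2 treats a condition as present when the patient carries any one of the listed ICD-10 codes.

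- **Lung disease.** The codes include "J80-84, J85-86, J90-91, J92.9, J93-94, J95-99". The included conditions end with "chronic lung diseases due to external agents, interstitial lung diseases, pleural diseases, respiratory failure". The exclusions are "acute respiratory infections, lung cancer, diseases of pulmonary circulation, pleural plaques without asbestos, previous uncomplicated pneumothorax". Acute respiratory infection is therefore excluded, but acute respiratory failure is not.
- **Cardiovascular disease.** The included conditions name "cardiovascular syphilis, endo-, myo- and pericarditis, rheumatic fever", among conditions described as chronic or likely to leave chronic sequelae.
- **Chronic kidney disease.** The codes include "N00-19, N20.0, N25-27, N28.0, N28.9, Q63.9, Z90.5". The only exclusion is clinically nonsignificant cysts.
- **Asthma.** Acute severe asthma stands under both the included and the excluded conditions.

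Annex 1, Section A asks about new or worsening dysfunction in ICU patients. It lists "Acute respiratory failure", ARDS, acute renal failure, and myocarditis or pericarditis.

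The chronic conditions are used twice: as populations of special interest in every secondary objective (section 14.2), and as adjustment factors (section 15.14.4.3).

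**The concern.** A baseline covariate should be fixed before the episode that defines case status. As worded, the lung, cardiovascular and kidney flags can be switched on by something that happens during that episode. The flag then partly measures severity.

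If vaccinated and unvaccinated cases differ in severity, they are sorted differently into the flagged and unflagged strata, and the stratum-specific CVE values move apart even when the true CVE is the same in everyone. A reader of the secondary results could take this for effect modification by chronic disease. The adjusted models and the case-control tables would also carry a variable measured after onset.

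The central analyst could not repair this. Sites transform their data locally to the common minimum dataset (section 15.13.1), and the Annex 4 comorbidity variables are coded no, yes or no information, with no diagnosis date.

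**Working it through.** **Step 1: what the text admits.** Respiratory failure, myocarditis and pericarditis are named in Annex 2 itself. ARDS within J80-84 and acute renal failure within N00-19 rest on the standard meaning of the codes. The kidney row has no list of included conditions.

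**Step 2: whether a date rule exists.**

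| Item | Reference time or acute exclusion |
|---|---|
| Iatrogenic immunodeficiency (Annex 2) | treatment in the three months before symptom onset |
| Cancer (Annex 2) | 5-year limit after curative treatment |
| Pregnancy (Annex 4) | at symptom onset |
| Chronic liver disease (Annex 2) | acute liver disease excluded |
| Lung disease | no date; acute respiratory infections excluded, respiratory failure included |
| Cardiovascular disease | no date |
| Chronic kidney disease | no date; no acute exclusion |

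The last three rows lack what the protocol supplies elsewhere.

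**Step 3: size of the possible distortion.** No figure in the protocol depends on this definition, so there is none to reproduce. The true CVE of 80% is one of the values in section 15.11.1.1. The prevalences and acute-code rates below are assumptions, because the protocol gives none.

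Let c be the true chronic prevalence, equal in all groups. Let a_v and a_u be the probabilities that a vaccinated or unvaccinated case without chronic disease receives an index-stay acute code. Suppose that the rate in controls does not depend on vaccination, so that it cancels. Then:

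- P(flag) = c + (1 − c)a
- flagged OR = OR_true × [c + (1 − c)a_v] / [c + (1 − c)a_u]
- unflagged OR = OR_true × (1 − a_v) / (1 − a_u)

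Worked case with c = 20%, a_u = 30%, a_v = 15%:

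- P(flag) is 0.2 + 0.8 × 0.15 = 0.32 in vaccinated cases and 0.2 + 0.8 × 0.30 = 0.44 in unvaccinated cases.
- Flagged OR = 0.2 × 0.32/0.44 = 0.145, so CVE = 85.5%.
- Unflagged OR = 0.2 × 0.68/0.56 = 0.243, so CVE = 75.7%.

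| c | a_u | a_v | CVE flagged | CVE unflagged | Gap (points, from unrounded values) |
|---|---|---|---|---|---|
| 20% | 20% | 15% | 82.2% | 78.8% | 3.5 |
| 20% | 30% | 15% | 85.5% | 75.7% | 9.7 |
| 20% | 40% | 20% | 86.2% | 73.3% | 12.8 |
| 40% | 30% | 15% | 83.1% | 75.7% | 7.4 |
| 40% | 30% | 30% | 80.0% | 80.0% | 0 |

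A steeper contrast (c = 40%, a_u = 50%, a_v = 20%) gives 85.1% and 68.0%. At a true CVE of 90%, with c = 40%, a_u = 30% and a_v = 15%, the values are 91.6% and 87.9%.

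**Step 4: only some sites use index codes.** Suppose one third of equally sized sites do so, at the 30%/15% rates with c = 20%. Merging all patients gives effective rates of 10% and 5%:

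- flagged OR = 0.2 × 0.24/0.28 = 0.171 (CVE 82.9%)
- unflagged OR = 0.2 × 0.95/0.90 = 0.211 (CVE 78.9%)

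The gap is about 4 points. Averaging the site log ORs with equal weights gives 82.0% and 78.7%, a gap of about 3 points.

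**Step 5: when equal rates are not enough.** Suppose chronic prevalence is 50% in vaccinated and 30% in unvaccinated controls, chronic disease doubles the case odds, and the acute-code rate is 20% in everyone. The flagged CVE is then 78.2%, the unflagged 80.0% and the adjusted 79.0%. A zero distortion in general therefore also needs chronic status to be unrelated to vaccination and case status.

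**Step 6: overall adjusted CVE.** With coverage of 80%, across the scenarios at a true CVE of 80% (including those with confounding and the steeper contrast), the Mantel-Haenszel adjusted CVE lies between 78.7% and 80.0%.

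**Step 7: with a pre-onset rule.** Setting a_v, a_u and the control rate to 0 returns 80.0% in both strata and overall, and 90.0% when the true CVE is 90%.

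**The case against.** The strongest reply is that the plan already means pre-existing disease. The Abstract asks for a history, Annex 2 is headed as chronic conditions, and section 15.14.4.4 says that covariate data often come from records that predate the SARI episode. The exclusion of previous uncomplicated pneumothorax and pulmonary embolism also reads like history-taking. Section 15.7 describes how patients are found retrospectively, not how comorbidities are dated, and sites document their own data flow.

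This stands as evidence of intent, and it rules out a stronger reading that a reader might infer: that the plan does record COVID-19 severity as baseline disease and that its CVE estimates are distorted. Nothing in the protocol says that index-stay codes count. Section 17 calls it unknown whether vaccination leads to milder disease, and the acute-code rates above are assumed. It would also be wrong to say that Annex 2 has no time limits at all, since immunodeficiency and cancer have them.

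The reply does not close the gap. A description of intent in the Abstract, and a remark made to support a missing-data assumption, are not coding rules. Data are retrieved from hospital databases at some sites (section 15.2), and covariates are collected for retrospective patients too (section 15.10), so index-stay codes are a foreseeable source.

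A further fair point is that deleting acute codes would discard genuine past disease, such as earlier myocarditis, which Annex 2 includes on purpose. That is accepted.

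**Conclusion.** The definitions should be corrected, but the defect is a risk to subgroup results and not an established bias. The lung, cardiovascular and kidney flags admit acute events that Annex 1 treats as complications of the current stay, and nothing in Annex 2 or Annex 4 dates them.

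The false gap between strata, about 3 to 13 points at a true CVE of 80%, rests on two assumptions: that index-stay codes are used at all sites, and that they are more frequent in unvaccinated than in vaccinated cases. The chronic-condition CVE of the secondary objectives is what is exposed; the overall adjusted estimate is little affected.

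The double listing of acute severe asthma is a separate contradiction in the text. It needs correction whatever its effect on CVE, which has not been shown.

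**What to change.** At the head of Annex 2 and in the Annex 4 comorbidity rows, state that a condition counts only if it was diagnosed or coded before the symptom onset date of the current SARI episode, and that codes first assigned during the index admission do not count. Existing treatment windows, such as the one for immunodeficiency, can stay. Once this rule applies, the acute codes need not be deleted. List acute severe asthma under the included or the excluded conditions, not both.

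The cost is a few lines of text and a date filter at sites that work from coded data; the onset date is already a mandatory variable in Annex 4. Recruitment began in September 2021 according to the Abstract, so sites that used coded data would need to confirm or re-derive flags already uploaded. The scientific downside is that chronic disease first recognised during the index stay will be missed.
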